6.6.3. Context and rationale for study exclusion criteria.....	14
6.6.4. Context and rationale for exposure(s) of interest.....	14
6.6.5. Context and rationale for outcome(s) of interest.....	15
6.6.6. Context and rationale for follow up.....	17
6.6.7. Context and rationale for covariates	17
6.7. Data analysis	22
6.7.1. Context and rationale for analysis plan	22
6.8. Study size and feasibility	32
7. Limitation of the methods.....	31
8. Protection of human subjects	31
9. References	32
10. Appendices	34
10.1. CONSORT diagrams	34
10.2. Covariate balance figures	37
10.3. Sample size/power calculations.....	40
10.4. Additional Figures and Tables	41

2. Abstract

This trial emulation study aims to emulate the PALOMA-2 trial (NCT01740427) using real-world specialty oncology electronic health records data and to investigate the concordance between the trial's original and the emulated treatment effect estimate on overall survival (OS). PALOMA-2 was a Phase III, randomized, double-blind study evaluating the efficacy and safety of palbociclib (125 mg orally, once daily for 21 days followed by 7 days off) in combination with letrozole (2.5 mg orally, once daily, continuously) versus placebo plus letrozole in postmenopausal women with estrogen receptor-positive (ER+), human epidermal growth factor receptor 2-negative (HER2-) advanced breast cancer who had not received prior systemic treatment for their advanced disease.

3. Amendments and updates

Version date	Version number	Section of protocol	Amendment or update	Reason
June 11, 2025	V1.0	NA	Initial version	NA
August 18, 2025	V1.1	4. Rationale and background 5. Research question and objective 6. Research methods	Refinement of text based on FDA feedback	NA
January 31, 2026	V1.2	6. Study design diagram	Study design diagram updated to explicitly reflect data vendor proprietary business rules for line-of-therapy assignment, exposure assessment window, and calendar year alignment; diagram now accounts for date imprecision between metastatic diagnosis and line of therapy initiation	To improve transparency and consistency with vendor-specific line-of-therapy definitions and real-world data timing constraints
		Table 5 (Covariates)	Added explicit covariate assessment window for c_number_met_sites	To align covariate derivation with vendor business rules governing line of therapy and metastatic timing

		Table 5 (Covariates)	Added explicit exposure assessment window definitions consistent with proprietary vendor rules	To ensure consistent exposure classification across databases
		Table 5 (Covariates)	Removed covariate dem_age_initial_diagnosis (Age at initial diagnosis)	Age at index date is already adjusted for; age at initial diagnosis adds redundancy without improving confounding control
		Table 5 (Covariates)	Removed covariate dem_sex (Sex)	Breast cancer trial population consists exclusively of women; adjustment for sex is unnecessary
		6.6.7 Context and rationale for covariates	Clarified rationale for excluding sex and age at initial diagnosis as covariates	To document alignment between clinical trial population, data structure, and analytic adjustment strategy
		6. Research methods / biomarker definitions	Introduced new function edbx_get_her2() implementing an algorithm based on ASCO HER2 testing guidelines	To improve accuracy and standardization of HER2 status classification across EHR data sources
February 9, 2026	V2.0	6.1.1, Table 7, Table 8 (Sensitivity analyses), 10.3 (Power)	EDB4 was excluded from the primary analysis and included in sensitivity analysis #11 (meta-analysis)	Because the study identification period (10/01/2018-09/30/2023) began after the 2017 approval of ribociclib, patients who initiated ribociclib before 10/01/2018 were only included if they survived until the start of the study period, which may introduce immortal time and selection bias due to left truncation.

4. Rationale and background

Randomized controlled trials (RCTs) are generally regarded as the gold-standard of evidence for establishing efficacy of medical products. However, real-world data (RWD) are increasingly used to complement evidence from RCTs. Yet, to have confidence in the accuracy of treatment efficacy estimates from RWD, investigators need to know what questions can be validly answered, with which non-interventional study designs, and which analysis methods are appropriate, given the data that is available. Building on a process from the RCT DUPLICATE initiative,¹⁻⁴ **Emulation of Comparative Oncology trials with Real-world Evidence (ENCORE)** is part of the expansion project specific to oncology and aims to emulate 12 randomized oncology RCTs using multiple EHR data sources.

The purpose of this protocol is to describe the emulation of the **PALOMA-2** trial. PALOMA-2 was a Phase III, double-blind, randomized study assessing the efficacy and safety of **palbociclib (125 mg orally, once daily for 21 days of a 28-day cycle) in combination with letrozole (2.5 mg orally, once daily, continuously) versus letrozole alone** in postmenopausal women with **estrogen receptor-positive (ER+), human epidermal growth factor receptor 2-negative (HER2–) advanced breast cancer** who had not received prior systemic treatment for their advanced disease.

The primary trial endpoint was **progression-free survival (PFS)** with a hazard ratio (HR) of **0.58** (95% CI, 0.46 to 0.72), based on a **median PFS of 24.8 months** (95% CI, 22.1 to not estimable) in the palbociclib-plus-letrozole group compared with **14.5 months** (95% CI, 12.9 to 17.1) in the letrozole-alone group. The FDA granted palbociclib accelerated approval in [February 2015](#), in combination with letrozole for the treatment of ER-positive, HER2-negative advanced breast cancer as initial endocrine based therapy in postmenopausal women.

Overall survival (OS) was a secondary trial endpoint with a hazard ratio of **0.96** (95% CI, 0.78 to 1.18; one-sided $p = 0.34$) based on a median OS of 53.9 months in the palbociclib-plus-letrozole group and 51.2 months in the letrozole-alone group.

The results of the PFS endpoint were published in the *NEJM* on November 17, 2016 ([PMID 27959613](#)).⁵

The final results of the OS endpoint were published in the *J. Clin. Oncol.* on January 22, 2024 ([PMID 38252901](#)).⁶

5. Research question and objectives

The primary and secondary research question is summarized in Table 1.

A. Primary research question and objective

Table 1. Primary and secondary research questions and objective.

Objective:	To compare the overall survival [OS] in patients who initiated palbociclib plus letrozole versus patients who initiated letrozole alone.
Hypothesis:	Initiation of palbociclib plus letrozole improves OS time as compared to initiation of letrozole alone.
Population (mention key inclusion-exclusion criteria):	
• Age ≥ 18 years• Postmenopausal women with ER-positive, HER2-negative locally advanced or metastatic breast cancer who receive treatment without curative intent
○ The line of therapy for patients in EDB1 and EDB3 is implicitly advanced/metastatic because the line of therapy classification starts after their advanced/metastatic diagnosis in the respective database○ In EDB4, patients must explicitly have any evidence of a metastasis prior initiating palbociclib plus letrozole or letrozole alone• Adenocarcinoma histology
• No prior systemic treatment for advanced/metastatic disease• ECOG 0 or 1
Exposure:	Initiation of palbociclib plus letrozole
Comparator:	Initiation of letrozole
Outcome:	Primary: Time to all-cause mortality (OS) Secondary: Time to next treatment (TTNT)
Time (when follow up begins and ends):	From the day of treatment initiation until outcome. Death, last observed clinical activity/last sign of the patient being alive, or data cut-off, whichever occurred earliest
Setting:	1L ER-positive, HER2-negative locally advanced or metastatic adenocarcinoma of the breast
Main measure of effect:	Hazard ratio (95% CI)

The emulation of the main protocol elements of the PALOMA-2 is illustrated side by side in **Table 2**.

Table 2. Trial emulation table summarizing the main protocol elements of the PALOMA-2 trial and the planned emulation.

Protocol component	PALOMA-2 RCT	Emulation	Comments
Eligibility criteria	
 • Women aged ≥ 18 years with diagnosis of breast cancer • Histologically or cytologically confirmed adenocarcinoma of the breast • Locoregionally recurrent or metastatic disease not amenable to curative resection/radiotherapy • ER-positive status • HER2-negative status • Postmenopausal status • No prior systemic therapy for advanced/metastatic ER+ disease • Measurable disease per RECIST v1.1 or bone-only disease confirmed by imaging • WHO/ECOG performance status 0 or 1 	
 • Female aged ≥ 18 years at treatment initiation with a diagnosis of breast cancer • Diagnosis of breast adenocarcinoma via histology/pathology records • Evidence of metastatic or recurrent disease • Documentation of ER-positive (or -missing) status • Documentation of HER2-negative (or -missing) status • N/A • No systemic anti-cancer therapy* following initial record indicating metastatic disease and prior to index date • N/A • WHO/ECOG performance status of 0 or 1 within 90 days of index date 	
 • If ER is missing and a patient received the exposures of interest, then ER is likely to be positive given the alignment with the indication for the exposures of interest • If HER2 is missing and a patient received the exposures of interest, then HER2 is likely to be negative given the alignment with the indication for the exposures of interest • Although not directly captured in RWD, it is likely to be fulfilled given the alignment with the indication for the exposures of interest • It is reasonable to assume that all patients in RWD had evidence of disease if they received treatment; additionally OS primary endpoint does not require measurable disease

- No symptomatic, life-threatening visceral disease (e.g., massive effusions, >50% liver involvement)

- N/A

- No active or symptomatic CNS metastases

- Record of CNS metastases prior to or on index date

- No prior treatment with CDK4/6 inhibitors

- Exclude patients with prior CDK4/6 inhibitor exposure

- No recurrence during or within 12 months of adjuvant non-steroidal AI (anastrozole or letrozole)

- Treatment with letrozole or anastrozole ≤ 12 Months prior to date of metastatic diagnosis

- No other malignancy within 3 years

- No prior record of non-breast malignancy within 3 years

- N/A

- Restriction to the time period 2015-2022

- This is a safety criterion for the trial and less relevant to real-world treatment setting, given that patients received treatments of interest

- 2015 was the approval year for palbociclib, and 2022 is when the final OS results of the competitor ribociclib were published⁷

Treatment strategies	Palbociclib + letrozole vs. placebo + letrozole	Patients initiating palbociclib + letrozole vs. letrozole alone, using an exposure assessment window to capture combination treatments, based on each data vendor's proprietary business rules	Use treatment start dates to define exposure
Assignment procedures	Randomized 2:1 to palbociclib + letrozole or placebo + letrozole	Propensity score-based matching or weighting to emulate randomization	Balance baseline covariates to reduce confounding
Follow-up period	Time from randomization to death or censoring	Time from treatment initiation to death or censoring	
Outcome	Primary: Progression-free survival (PFS) per investigator assessment Secondary: Overall survival (OS)	Primary: OS Secondary: Time-To-Next-Treatment (TTNT)	Lack of good measurement of progression, so inferred by initiation of next treatment as a secondary endpoint rather than primary
Causal contrast	Intent-to-treat effect	Effect of initiating palbociclib + letrozole versus letrozole	Analogous to ITT; emulates initiation rather than adherence

*Includes the following: apelisib, capecitabine, carboplatin, cisplatin, cyclophosphamide, docetaxel, doxorubicin, epirubicin, eribulin, exemestane, fluorouracil, gemcitabine, goserelin, ixabepilone, methotrexate, olaparib, paclitaxel, tamoxifen, talazoparib, toremifene, and vinorelbine.

6. Research methods

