- **EDB4:** Time in [days, months and years] from index date to death due to any reason. The date of death is de-identified to month-level granularity and the day of death is therefore imputed to the 15th of a month. If there is no indication that a patient died during the study period, the patient is censored. The censoring date is defined as the last date of vital signs recorded as proof that the patient was alive at that time (de-identified to week-level granularity) or data cut-off date, whichever occurred earlier. The OS endpoint is operationalized using a parameterized R function *edb4_get_os()* and more details can be found in the attached pdf documentation.

Table 4. Relevant clinical activities considered to derive last activity date for censoring.

Table / clinical activity considered	Dates considered
Adverse events	Event date
Therapy (cellular, systemic, radiation, surgery)	Start and end dates or declined intervention date, surgery date, assessed resection dates
Palliative care referral	Referral date
Visits	Contact/visit date
Vitals	Assessed date
Labs	Lab date
Biomarkers	Specimen collection date
Patient observation period	Start and end dates

Demographics	Date of most recent contact with provider, date patient was diagnosed with a second primary malignancy
Performance assessments	Documented date, reported date
Secondary diagnoses	Diagnosis date
Progression, histology, lymphovascular invasion, metastatic sites, pancoast tumor, perineural invasion	Assessed date
Stage/TNM	Assessed date
Smoking	Assessed date

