Socio-economic status	dem_ses	edbx_get_demographics()	Socioeconomic status (SES) index based on residence area of patient. Not available in EDB3 and EDB4.	Nominal (from '1 - Lowest SES' through '5 - Highest SES')	[-inf;0]
Smoking	c_smoking_history	edbx_get_demographics()	History of current or former (= TRUE) or never (= FALSE) smoking on or anytime before index date; if there are multiple records per patient, any evidence of former/current smoking is prioritized. IN EDB1, "smoking history" is not available for breast cancer.	Binary logical (TRUE, FALSE)	[-inf;0]
ECOG	c_ecog	edbx_get_ecog()	ECOG performance status measured closest to index date within assessment window. In	Nominal (0, 1, 2, 3, 4); modelled as ordinal numeric in ROPRO ¹⁰ ; due to I/E	[-90;0]

Characteristic	Harmonized analysis variable name	R function to derive covariate (see pdf in appendix)	Details ¹	Variable encoding	Assessment window
			case of ties, the lower ECOG value is selected	criteria ECOG is modelled as a binary (0, 1) covariate	
Stage	c_stage_initial_dx	edbx_get_diagnosis_solid()	AJCC summary group stage at initial diagnosis	Ordinal numeric (from 0 to IV with sub-categories, e.g., IA1) ¹⁰	[-inf;0] at initial diagnosis of primary cancer
De novo metastatic status	c_de_novo_mets_dx	edbx_get_diagnosis_solid()	Evidence of presence of one or multiple metastases at/before initial diagnosis	Binary logical (TRUE, FALSE)	[-inf;0] at initial diagnosis of primary cancer
Number of metastatic sites	c_number_met_sites	edbx_get_diagnosis_solid()/edbx_get_number_met_sites_solid()	Number of metastatic sites for a given patient before/on index date	Integer	[-inf;X]; Proprietary business-rule-based covariate assessment window
Time between initial diagnosis to index date	c_time_dx_to_index	edbx_get_diagnosis_solid()	Time in days between initial diagnosis to index date. Quartiles will be used because there may be “negative” times intervals due to date imprecision of the lines of therapy.	Categorical (quartiles)	[-initial dx;0]
Time between earliest evidence of a metastatic and index date	c_time_met_dx_to_index_quartiles	edbx_get_diagnosis_solid()	Time in days between earliest evidence of a metastatic diagnosis and index date. Quartiles will be used because there may be “negative” times intervals due to date imprecision of the lines of therapy.	Categorical (quartiles)	[met dx;0]

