Inclusion	All patients must agree to provide tumor tissues for centralized retrospective confirmation of ER status and to evaluate correlation between genes, proteins, and RNAs relevant to the cell cycle pathways and sensitivity/resistance to the investigational agents. Freshly biopsied, recurrent/metastatic tumor samples must be provided whenever possible. If such a biopsy is not feasible or cannot be safely performed, then an archived tumor sample may be accepted. In either case a formalin fixed, paraffin embedded (FFPE) block or 12 unstained FFPE slides are required for patient participation.	Limited relevance	Not implementable	Not implementable	Not implementable	Not applicable
Inclusion	Evidence of a personally signed and dated informed consent document indicating that the patient (or a legal representative) has been informed of all pertinent aspects of the study before any study-specific activity is performed.	Limited relevance	Not implementable	Not implementable	Not implementable	Not applicable
Inclusion	Restriction to period 2015-2022	Relevant	Possible	Possible	Possible	2015 was the approval year for palbociclib, and 2022 is when the final OS results of the competitor ribociclib were published
Exclusion	HER2-positive breast cancer	Relevant	Possible	Possible	Possible	
Exclusion	Patients with advanced, symptomatic, visceral spread, that are at risk of life-threatening complications in the short term (including patients with massive uncontrolled effusions [pleural, pericardial, peritoneal], pulmonary lymphangitis, and over 50% liver involvement).	Relevant	Limited	Limited	Limited	We assume that if they are treated, they do not meet this exclusion criterion
Exclusion	Known active uncontrolled or symptomatic CNS metastases, carcinomatous meningitis, or leptomeningeal disease as indicated by clinical symptoms, cerebral edema, and/or progressive growth. Patients with a history of CNS metastases or cord compression are eligible if they have been definitively treated with local therapy (eg, radiotherapy, stereotactic surgery) and are clinically stable off anticonvulsants and steroids for at least 4 weeks before randomization.	Relevant	Possible	Possible	Possible	Record of CNS metastases

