Exclusion 1	HER2-positive breast cancer	$[-\infty; 0]$	Any HER2+ status prior to or on index date	Any HER2+ status prior to or on index date	Any HER2+ status prior to or on index date	If HER2 is missing and a patient received the exposures of interest, then HER2 is likely to be negative given the alignment with the indication for the exposures of interest	edbx_get_her2()
Exclusion 2	Patients with advanced, symptomatic, visceral spread, that are at risk of life-threatening complications in the short term (including patients with massive uncontrolled effusions [pleural, pericardial, peritoneal], pulmonary lymphangitis, and over 50% liver involvement).	NA	NA	NA	NA	This is a safety criterion for the trial and less relevant to real-world treatment setting, given that patients received treatments of interest	
Exclusion 3	Known active uncontrolled or symptomatic CNS metastases, carcinomatous meningitis, or leptomeningeal disease as indicated by clinical symptoms, cerebral edema, and/or progressive growth. Patients with a history of CNS metastases or cord compression are eligible if they have been definitively treated with local therapy (eg, radiotherapy, stereotactic surgery) and are clinically stable off anticonvulsants and steroids for at least 4 weeks before randomization.	$[-\infty; 0]$	Record of CNS metastases prior to or on index date	Record of CNS metastases prior to or on index date	Record of CNS metastases prior to or on index date		edbx_get_diagnosis_solid()
Exclusion 4	Prior neoadjuvant or adjuvant treatment with a non-steroidal aromatase inhibitor (ie, anastrozole or letrozole) with disease recurrence while on or within 12 months of completing treatment.	[MBC-365; MBC-1]	Treatment with letrozole or anastrozole ≤ 12 months from MBC	Treatment with letrozole or anastrozole ≤ 12 months from MBC	Treatment with letrozole or anastrozole ≤ 12 months from MBC		
Exclusion 5	Prior treatment with any CDK4/6 inhibitor.	$[-\infty; -1]$	Prior treatment with ribociclib, palbociclib, abemaciclib	Prior treatment with ribociclib, palbociclib, abemaciclib	Prior treatment with ribociclib, palbociclib, abemaciclib		
Exclusion 6	Major surgery, chemotherapy, radiotherapy, any investigational agents, or other anti-cancer therapy within 2 weeks before randomization. Patients who received prior radiotherapy to 25% of bone marrow are not eligible independent of when it was received (see Appendix 4).	NA	NA	NA	NA		Proxied by 1st line therapy inclusion

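### Table 5 has no covariate for where the metastases are, so visceral versus bone-only disease is balanced only indirectly in the primary OS comparison

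*Combined protocol and SAP*

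**What the plan says.** Two trial criteria that touch on disease location are set to N/A in Table 2 (section 5) and in Excel appendix Table 2, for all three databases.

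- **Life-threatening visceral spread (trial exclusion).** Table 2 and Excel appendix Table 2 give the same reason: "This is a safety criterion for the trial and less relevant to real-world treatment setting, given that patients received treatments of interest". Excel appendix Table 1 rates the criterion Relevant, with emulation Limited, and adds: "We assume that if they are treated, they do not meet this exclusion criterion".
- **Measurable or bone-only disease (trial inclusion).** The trial required "Measurable disease per RECIST v1.1 or bone-only disease confirmed by imaging". Table 2 waives this because "It is reasonable to assume that all patients in RWD had evidence of disease if they received treatment", and also because an OS endpoint does not need measurable disease.

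On adjustment, the one variable in Table 5 (section 6.6.7) that describes metastatic extent is an integer: "Number of metastatic sites for a given patient before/on index date". Table 5 also lists stage at initial diagnosis, de novo status, timing variables, ECOG, labs and vitals. It has no visceral, liver, lung, bone or bone-only entry. The only site-specific rule is the CNS exclusion in Excel appendix Table 2: "Record of CNS metastases prior to or on index date".

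**The concern.** In the trial, randomisation balanced the location of disease whether or not anyone recorded it. In the emulation that task falls to the propensity score, and matching guarantees nothing for a variable outside the model. Location plausibly affects both whether palbociclib is added to letrozole and how long the patient lives, which would make it a confounder of the primary OS hazard ratio. Balance figures restricted to Table 5 covariates would not show an imbalance in it.

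The target is an OS HR of 0.96, so a distortion of about 4% is as large as the effect being reproduced. The stated purpose is concordance with that near-null result, and section 10.3 expects a tighter interval than the trial's in the larger database. A small systematic shift could therefore be read as agreement or disagreement with the trial.

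**Working it through.** **Step 1. Is location covered anywhere in the plan?**

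| Place | Location of disease |
|---|---|
| Table 2 and Excel appendix Table 2 | Visceral and measurable/bone-only criteria N/A; CNS metastases excluded |
| Table 5 | Count of sites only |
| Table 7 subgroups | Age, region, ECOG, disease-free interval; no location |
| Table 8, sensitivity #6 (re-weighting to the trial) | Refers to the Table 7 subgroups; no location |
| Table 8, other sensitivity analyses | None names location |
| Section 7 | Missing data and data continuity only |

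**Step 2. Precision of the primary analysis.** Section 10.3 assumes alpha 0.05, 50% exposed and HR 0.92, with 1021 events in EDB1 and 331 in EDB3. The Schoenfeld power is Φ(√(events × 0.25) × |ln 0.92| − 1.96).

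- EDB1: 15.98 × 0.0834 − 1.96 = −0.63, power 0.265 (stated 0.27).
- EDB3: 9.10 × 0.0834 − 1.96 = −1.20, power 0.115 (stated 0.11).

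Both stated figures reproduce as two-sided. Pooled events are 1021 + 331 = 1352, so SE(log HR) ≈ 2/√1352 = 0.054. A 95% CI centred on 0.96 would run from about 0.86 to 1.07.

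**Step 3. Size of a possible distortion.** For one omitted binary covariate, the approximate bias factor is [1 + p1(h − 1)] / [1 + p0(h − 1)]. Here p1 and p0 are the prevalences of visceral disease after matching in the palbociclib-plus-letrozole and letrozole-alone arms, and h is its mortality HR. The documents give none of the three, so all values below are assumptions.

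| p1, p0 | h | Factor | 0.96 reads as | Factor with p1 and p0 swapped | 0.96 reads as |
|---|---|---|---|---|---|
| 0.50, 0.40 | 1.5 | 1.25/1.20 = 1.042 | 1.00 | 0.960 | 0.92 |
| 0.50, 0.40 | 1.8 | 1.40/1.32 = 1.061 | 1.02 | 0.943 | 0.91 |
| 0.50, 0.35 | 1.5 | 1.25/1.175 = 1.064 | 1.02 | 0.940 | 0.90 |
| 0.50, 0.35 | 1.8 | 1.40/1.28 = 1.094 | 1.05 | 0.914 | 0.88 |

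In pooled standard errors, ln(1.042)/0.054 ≈ 0.8 and ln(1.094)/0.054 ≈ 1.7.

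The result depends on the inputs. A 5-point gap (0.45 against 0.40) with h = 1.3 gives 1.135/1.12 = 1.01. A 20-point gap (0.55 against 0.35) with h = 2.0 gives 1.55/1.35 = 1.15, or 0.87 reversed.

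**Step 4. Could location be derived?** The CNS exclusion is rated Possible in all three databases and is run through edbx_get_diagnosis_solid(). Table 5 lists that function as one of two for the site count. Table 4, which section 6.6.5 cites for EDB3, has a dated source described as "Progression, histology, lymphovascular invasion, metastatic sites, pancoast tumor, perineural invasion". So some site-level information is already being read, but the documents do not describe its completeness in EDB1 or EDB3.

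**The case against.** A reader might infer more than the documents support, in four ways.

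- **That the waivers dropped a visceral-versus-bone-only restriction.** They did not. The trial excluded only symptomatic visceral spread that threatened life in the short term, and its measurable/bone-only criterion admits both kinds of disease. A visceral yes/no flag would not emulate the waived exclusion. The trial also enrolled patients for whom chemotherapy was not indicated, so receiving first-line endocrine-based therapy is a partial proxy for the absence of that severe presentation. The gap is the missing covariate.
- **That location is certainly absent from every fitted propensity model.** Table 5 is titled as key covariates, section 6.6.7 promises the most comprehensive model per database, and Figures 7 to 9 are not available here. What can be said is that Table 5 does not list it.
- **That the location data are known to be usable.** Finding a CNS record does not show that the absence of non-bone sites is reliably captured, which a bone-only flag requires. Table 4 lists dates used for censoring and includes items from other tumours.
- **That the OS hazard ratio is biased, in a known direction.** No document gives the imbalance or the prognostic strength. Site count, ECOG, ALP, AST, ALT, bilirubin, LDH and albumin would absorb part of any imbalance.

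Rating a criterion Relevant but Limited and covering it with a disclosed assumption is also consistent with section 6.6.3, which emulates criteria that are both relevant and measurable.

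All of this stands, and it narrows the point. It does not fill the gap: proxies are not the variable, and an assumption satisfied by treatment in both arms says nothing about balance between them.

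**Conclusion.** The point holds as a gap in the adjustment plan. As written, Table 5 leaves a plausible strong confounder of the primary OS HR adjusted only indirectly, and no subgroup, sensitivity analysis or limitation addresses it.

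The size is illustrative. It rests on the assumed prevalences and mortality HR, on the imbalance surviving matching on the proxies, and on a formula for a single binary factor with no interaction. Under the 10-to-15-point scenarios a true 0.96 would read as about 1.00 to 1.05, or about 0.88 to 0.92 if letrozole-alone patients carry more visceral disease. Those values lie inside the trial's interval of 0.78 to 1.18 and inside the pooled interval in step 2, so the confidence interval would not signal the shift.

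Separately, Excel appendix Table 1 calls the visceral-spread criterion relevant, while Table 2 and Excel appendix Table 2 call it less relevant. The two statements must be reconciled.

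**What to change.** 1. State for EDB1, EDB3 and EDB4 whether the records behind the CNS exclusion and the site count identify liver, lung/pleura, peritoneum and bone, and how complete they are.
2. Where they do, derive two baseline indicators on or before index: visceral metastasis (liver, lung/pleura or peritoneum; yes/no) and bone-only disease (yes/no). Add both to Table 5, the imputation model, the propensity score and the balance figures.
3. Where they do not, say so in section 7 and give a quantitative bias analysis like step 3 of the working, over both directions and a stated range of prevalence and hazard ratio.
4. Reconcile the two relevance statements for the visceral-spread criterion, stop using receipt of treatment as evidence that it is met, and list its waiver as a limitation in section 7.

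The cost is two derived variables per database, probably from tables already read, plus wording changes. The downside is slightly fewer matched pairs and some site-level missingness to impute. If site records prove too incomplete, item 3 costs only a short calculation.
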